4 POPULATIONS FOR ANALYSIS

4.1 Modified Intent-to-Treat Analysis Population

The mITT analysis population will include all randomized patients who receive at least one dose of study drug and have at least 1 post-treatment SALT assessment. Patients will be summarized according to study drug regimen to which they were randomized. This analysis population will be the main analysis population for the efficacy analyses.

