Patient safety will be monitored throughout the trial. The subject will be tested to ensure they do not have the Hepatitis B or C virus, thyroid function abnormalities or latent or active Tuberculosis, during the screening period. During the first 8 weeks of the Treatment Period, hematology and serum chemistry will be conducted every 2 weeks, followed by an assessment every 4 weeks thereafter through completion of the study at 24 weeks. Lipid levels will be assessed every 12 weeks throughout the Treatment Period. Significant cytopenias or other hematologic abnormalities will be managed by severity through dose interruption, or discontinuation, and signs and symptoms of infection will be closely monitored and treated promptly. Periodic skin examinations are recommended to detect non-melanoma skin cancers including basal cell, squamous cell and Merkel cell carcinoma. Patients who experience intolerable symptoms during treatment may discontinue the study at the discretion of the Investigator. Patients may withdraw consent at any time.

The Treatment Period will last 24 weeks to assess BID and QD doses, in parallel. Assessment of treatment response with SALT for efficacy will occur at 4, 8, 12, 16, 20 and 24 weeks.

Upon completion of the 24-week Treatment Period patients will be eligible to either complete treatment and exit the study following the safety follow-up visit, or roll-over into an open-label extension study.

Approximately 60 patients are planned to be enrolled in the study; approximately 30 patients per treatment arm.

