#### 7.3.1. **Patient Withdrawal Procedures**

A patient who prematurely discontinues study treatment/study participation should have all Week 24 assessments performed as an Early Termination Visit, and return for the Safety Follow-up Visit (See Table 1). The Safety Follow-Up Visit may be waived by the Sponsor in instances where patients have discontinued dosing prior to the Early Termination Visit on a case-by-case basis.

If a patient terminates early from the study, the Investigator will record the reason(s) for early termination on the relevant electronic case report form (eCRF). The specific reason for the withdrawal should be carefully documented on the eCRF.

Patients who require a dose interruption lasting more than 21 consecutive days for management of adverse events should be discontinued from the study. Adverse events resulting in patient early termination will be followed to the satisfactory resolution and determination of outcome, as ascertained by the Investigator (and/or Sponsor, or its designee); See Section 10 Adverse Events. The data will be recorded on the appropriate eCRF.

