### 11.3. Analysis Populations

The modified Intent-to-Treat (mITT) Population will include all patients who receive study drug and have at least 1 post-treatment SALT assessment. Patients will be summarized according to study drug regimen to which they were randomized. A Per Protocol Population may be defined prior to blind break if >10% of patients have clinically significant protocol deviations. The Safety Population will include all patients who receive study drug. Patients will be summarized according to study drug regimen received (i.e., as treated) should it differ from the randomized arm.

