4.2 Per Protocol Analysis Population

The Per Protocol (PP) analysis population will include all mITT subjects with no major protocol deviation (i.e., a major protocol deviation is defined as a protocol deviation that may alter or confound interpretation of the study results). The classification of each protocol deviation as major or not will be done prior to the database lock. Analyses based on this analysis population will be performed only if 10% or more of mITT patients have at least one major protocol deviation. Patients will be summarized according to study drug regimen to which they were randomized. This analysis population will be used to perform supportive efficacy analyses.

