6.3 Handling of Dropouts or Missing data

See Appendix 3 for handling of completely or partially missing dates for prior and concomitant medications and AEs. Imputed AE onset and end dates/medication start and stop dates will only be used for the determination of the treatment-emergent/concomitant status. That is, they will not be used to compute any study day or duration and will not be presented in the by-patient data listings.

For the SALT endpoints (e.g., absolute and percent changes from baseline as well as achieving at least 50%, 75%, 80%, and 90% reduction and having a SALT score ≤ 10 and ≤ 20, the Last Observation Carried Forward (LOCF) approach will be implemented for missing SALT score data, e.g., if the SALT score in the Week 16 visit window is missing, the next and closest available ontreatment SALT score measurement before the Week 16 visit window will be used for all remaining SALT assessments: Week 16, Week 20 and Week 24. Missing baseline values will not be carried forward. If a SALT assessment is missing between two non-missing SALT assessments visits, the SALT score at that visit will be interpolated using the mean of the closest pre- and post-assessments.

All other missing efficacy data as well as missing safety data will not be imputed.

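### Dosed patients with no SALT after dosing are left out of every planned efficacy analysis, so SALT responder rates can be overstated if there are any such patients

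*SAP*

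**What the plan says.** SAP 4.1 restricts the modified intent-to-treat (mITT) population to "all randomized patients who receive at least one dose of study drug and have at least 1 post-treatment SALT assessment" and gives it the leading role: "This analysis population will be the main analysis population for the efficacy analyses". Protocol 11.3 sets the same condition, "all patients who receive study drug and have at least 1 post-treatment SALT assessment", and the protocol synopsis repeats it under the name Efficacy Population. The SAP is therefore following the protocol here.

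Other provisions decide who is affected:

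- **SALT schedule.** Protocol 6.3: "Assessment of treatment response with SALT for efficacy will occur at 4, 8, 12, 16, 20 and 24 weeks". The schedule of events shows no SALT at Week 2.
- **Early leavers.** Protocol 7.3.1 says a patient who discontinues prematurely "should have all Week 24 assessments performed as an Early Termination Visit". SALT is among the Week 24 assessments.
- **Denominator.** SAP 6.2 bases percentages on the number of patients in the analysis population concerned, unless otherwise indicated.
- **Missing SALT.** SAP 6.3 carries forward an earlier on-treatment SALT and adds "Missing baseline values will not be carried forward".
- **Supportive population.** The Per Protocol population "will include all mITT subjects with no major protocol deviation" (SAP 4.2), so it is a subset of mITT.
- **Early Termination data.** SAP 5.4 summarises them as a separate visit.

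**The concern.** Being in the main efficacy population depends on a post-randomisation event. A dosed patient with no later SALT is not counted as a treatment failure in the 50, 75, 80 and 90% responder endpoints or in the SALT ≤10 and ≤20 endpoints. The patient simply disappears from them. LOCF cannot help, because there is no on-treatment value to carry. The main, supportive and subgroup SALT analyses in SAP 12.1, 12.2, 12.4 and 12.5 all use mITT or its Per Protocol subset.

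The trial exists to compare two regimens on efficacy and tolerability, and the estimated regimen difference is its main efficacy result. If early losses differed between regimens, the efficacy comparison would no longer be between the groups as randomised and dosed. The regimen with more such losses would look better than it does when those patients count as non-responders.

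**Working it through.** **The plan's own figure.** SAP 6.1 and Protocol 11.1 call 25 completers per group adequate. This cannot be reproduced, because no standard deviation (SD) or target interval width is given. Set against about 30 randomised per group, it implies 1 − 25/30 = 16.7% non-completion, or 5 per arm. That covers all non-completion. It is not a count of patients without any post-dose SALT, and the documents give no such count.

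**Inputs.**
- n = 30 treated per arm (about 30 randomised: SAP 3.1, Protocol 6.3).
- r = 12 responders per arm (40%). This is an assumption. The protocol gives no planning rate for either regimen; it reports 47% for 8 mg BID in the earlier study.
- k = number of dosed patients in an arm with no post-dose SALT. This is an assumption, taken as 0 to 3.
- Two-sided 90% interval (SAP 6.4); Wald with continuity correction (1/n1 + 1/n2)/2 (Protocol 11.4.2, SAP 12.2.1).

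**Overstatement within an arm** = r/(30 − k) − r/30:

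| k | mITT rate | All dosed, excluded counted as non-responders | Overstatement (points) |
|---|---|---|---|
| 0 | 12/30 = 40.0% | 40.0% | 0 |
| 1 | 12/29 = 41.4% | 40.0% | 1.4 |
| 2 | 12/28 = 42.9% | 40.0% | 2.9 |
| 3 | 12/27 = 44.4% | 40.0% | 4.4 |

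The size grows with the response rate. With 14 of 30 responders (46.7%, close to the 47% above) the overstatement is 1.6, 3.3 and 5.2 points for k = 1, 2 and 3. As an extreme, if all 5 implied non-completers in an arm had no SALT, 12/25 = 48.0%, which is 8.0 points.

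**Regimen difference.**
- *All losses on one arm, 12 responders in each:* a difference of 0 becomes 1.4, 2.9 or 4.4 points in favour of the arm with the losses.
- *Equal losses, equal response:* with 3 per arm, 12/27 − 12/27 = 0.
- *Equal losses, unequal response:* 14/30 − 10/30 = 13.3 points becomes 14/27 − 10/27 = 14.8 points.

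**Set against precision.** At 12/30 in each arm the standard error is √(2 × 0.4 × 0.6/30) = 0.1265 and the correction is (1/30 + 1/30)/2 = 0.0333. The half-width is 1.645 × 0.1265 + 0.0333 = 0.241, or about 24 points.

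**Primary endpoint.** If the mean relative change is 40% among 28 observed patients and two excluded patients are given zero change, the mean over 30 is 40 × 28/30 = 37.3%, a shift of 2.7 points. At an assumed SD of 30, the 90% half-width for the difference in means with 30 per arm is 12.9 points. It is 10.8 to 17.3 points for SDs of 25 to 40.

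**The case against.** The strongest reply is that the excluded group may be empty. A patient who stops early is directed to an Early Termination visit that includes SALT, and one SALT there meets the mITT condition. Exclusion needs both an early stop and no SALT at that visit. This stands, and it is why the point is conditional. It does not remove the gap: patients lost to follow-up or withdrawing consent may never attend. Attendance does not settle the matter either, because SAP 5.4 sets Early Termination data apart as their own visit and SAP 6.3 carries forward only on-treatment scores. A patient whose only SALT is at Early Termination could sit in the mITT denominator with no defined value at Weeks 4 to 24.

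Second, comparisons are for estimation, with no formal tests. Disposition tables give Safety and mITT counts by regimen, and tolerability is analysed in all treated patients. A reader could see an imbalance and recompute the responder rates. That limits the harm, but it does not correct the estimate that will be reported.

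A reader might go further and infer that early intolerance on one regimen will be removed from the comparison and that response rates are therefore inflated. The documents do not support that. They give no early-loss rate and no difference by regimen. Patients stopping for adverse events are among those directed to the Early Termination visit. Protocol 4.2.1 describes 12 mg BID as generally well tolerated to date. Its suggestion that once-daily dosing may be better tolerated rests on healthy-volunteer data for ruxolitinib and does not show who would miss a SALT.

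The SAP 6.3 sentence on baseline values is also weak support for the exclusion. Read literally, it concerns missing baselines and does not clearly bar carrying an observed baseline forward.

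**Conclusion.** The gap is real but conditional. The plan has no efficacy analysis that includes a dosed patient without a post-dose SALT. If such patients exist, responder rates can only equal or exceed the rates obtained by counting them as non-responders: by 1.4 to 4.4 points for 1 to 3 patients in an arm of 30 with 12 responders. The regimen difference can move either way, depending on which arm loses more. It moves little under equal loss and not at all if nobody is lost.

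These figures rest on assumed loss counts and an assumed 40% response. They lie well within the half-width of about 24 points, so on their own they are unlikely to change the reading of the trial. The point is worth acting on because the correction is cheap and removes an avoidable source of bias. Counting an unobserved patient as a non-responder is a conservative convention that suits the responder endpoints. Zero change for the continuous endpoints is a stronger imputation choice and belongs in a sensitivity analysis.

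**What to change.** 1. **Responder endpoints** (at least 50, 75, 80 and 90% reduction; SALT ≤10 and ≤20). Use all randomised patients who took at least one dose and have a baseline SALT, analysed as randomised. Count those with no post-baseline SALT as non-responders at every visit.
2. **Relative and absolute change.** Keep mITT as the main analysis. Add a prespecified sensitivity analysis in all dosed patients with a baseline SALT, with change set to zero where no post-baseline SALT exists. Reword the SAP 6.3 sentence on baseline values so that it does not appear to forbid this.
3. **Early Termination SALT.** State in SAP 5.4 and 6.3 whether it feeds LOCF, for which visits, and whether it counts as on-treatment when dosing stopped earlier.
4. **Record the change in SAP 3.4**, because item 1 departs from the population in Protocol 11.3. SAP 1 allows changes to be documented before database lock.

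Cost: SAP wording, a derivation rule and one added analysis, with no new data. The downside is slightly lower response estimates if any such patients exist.

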4.2 Per Protocol Analysis Population

The Per Protocol (PP) analysis population will include all mITT subjects with no major protocol deviation (i.e., a major protocol deviation is defined as a protocol deviation that may alter or confound interpretation of the study results). The classification of each protocol deviation as major or not will be done prior to the database lock. Analyses based on this analysis population will be performed only if 10% or more of mITT patients have at least one major protocol deviation. Patients will be summarized according to study drug regimen to which they were randomized. This analysis population will be used to perform supportive efficacy analyses.

4.3 Safety Analysis Population

The Safety analysis population will include all patients who received at least one dose of study drug. Patients will be summarized according to study drug regimen received (i.e., as treated) should it differ from the randomized study drug regimen.

	STATISTICAL ANALYSIS PLAN, Final v1.0
Protocol Number CP543.2003	Sponsor: Concert Pharmaceuticals, Inc.

5 GENERAL CONSIDERATIONS

Formats and layouts of tables, listings, and figures (TLFs) will be provided in a separate document (output general layout is described in Appendix 2). Minor changes to the mocks after formal SAP approval will not necessitate re-approval unless changes to the text of the SAP are required.

5.1 Baseline

Unless otherwise specified, Baseline value will be defined as the last non-missing assessment prior to the first dose of study drug (including repeat and unscheduled assessments). If the last non-missing assessment is performed on the same date as the first dose of study drug and time is not available, the assessment will be considered as Baseline, except for adverse events (AEs) and medications starting on the first study treatment dose date which will be considered post-Baseline.

5.2 Reference Start Date and Study Day

Study days will be calculated from the date of the first dose of study drug regimen and will be used to show start/end day of assessments or events.

Study day = (Date of event – Date of first dose) + 1 if date of event is on or after the date of first dose of study regimen;

= (Date of event – Date of first dose) if date of event is before the date of first dose of study regimen;

In situations where the assessment/event start/end date is partially or completely missing, study start/end day will be missing.

5.3 Windowing Conventions

For scheduled visits, there will be no reassignment of the analysis visit based on date, and all data will appear in summary tables based on the nominal timepoint.

Both unscheduled visits and repeat visits will be reassigned to the closest prior visit. If an assessment was already documented at that visit, the scheduled data will be used in summaries. If the scheduled data was missing, then the re-assigned unscheduled visit/repeat visit will be used in summaries.

5.4 Handling of Repeats, Unscheduled Visits, and Early Termination Data

See Section 5.3 for handling of unscheduled and repeat visits.

	STATISTICAL ANALYSIS PLAN, Final v1.0
Protocol Number CP543.2003	Sponsor: Concert Pharmaceuticals, Inc.

Early termination visit assessments will be summarized as a separate visit.

All data from repeat, unscheduled visits, and early termination visits will be listed.

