### 11.1. Sample Size Rationale

A sample size of 25 patients (completers) per group provides adequate precision for the estimated dosing regimen difference for relative change in SALT score from baseline at Week 24. Precision of the estimated difference is quantified by the width of the confidence intervals for the dosing regimen difference.

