	 Subgroup analyses: using LOCF imputation based on mITT analysis population within each subtype of alopecia areata at Baseline 	
Change from Baseline in satisfaction of hair coverage to Week 24	Baseline and Week 24	Descriptive statistics by visit and dosing regimen with difference in means and two-sided 90% CI (t-distribution) for each post-baseline visit
		• Main analysis: with no imputation based on mITT analysis population
		 Additional analysis: shift from baseline (satisfied vs. dissatisfied) to each post-baseline visit with no imputation based on mITT analysis population
		No supportive and subgroup analyses

	STATISTICAL ANALYSIS PLAN, Final v1.0
Protocol Number CP543.2003	Sponsor: Concert Pharmaceuticals, Inc.

Efficacy Endpoint	Collection Time	Method
Exploratory		
Change from Baseline in VAS for Eyebrows to Week 24	Baseline and Week 24	Descriptive statistics by visit and dosing regimen for each eyebrow separately with difference in means and two-sided 90% CI (t-distribution) for each post-baseline visit
		• Main analysis: with no imputation based on mITT analysis population
		No supportive and subgroup analyses
Change from Baseline in satisfaction of hair	Baseline and Week 24	Descriptive statistics by visit and dosing regimen with difference in means and two-sided 90% CI (t-distribution) for each post-baseline visit
coverage quality to Week		• Main analysis: with no imputation based on mITT analysis population
24		No supportive and subgroup analyses
Other		
Responder (80%) in relative change from Baseline in SALT score at	Baseline and Weeks 4, 8, 12, 16, 20, and 24	Count and proportion of subjects by visit and dosing regimen for each responder definition separately with difference in proportions and two-sided Wald 90% CI for each post-baseline visit
Weeks 4, 8, 12, 16, 20, and 24		 Main analysis: using LOCF imputation based on mITT analysis population
		• Supportive analysis: using LOCF imputation based on PP analysis population, if applicable
		• Subgroup analyses: using LOCF imputation based on mITT analysis population within each subtype of alopecia areata at Baseline

	STATISTICAL ANALYSIS PLAN, Final v1.0
Protocol Number CP543.2003	Sponsor: Concert Pharmaceuticals, Inc.

Efficacy Endpoint	Collection Time	Method

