14 APPENDICES

Appendix 1

Table 1 provides a description of the procedures planned at each visit.

	STATISTICAL ANALYSIS PLAN, Final v1.0
Protocol Number CP543.2003	Sponsor: Concert Pharmaceuticals, Inc.

Table 1: Schedule of Events

	Screening	Randomization ¹ Day 1 ² (Visit 2)	Treatment Period					Safety Follow-Up
Event	Day -28 to Day -1 (Visit 1)		Week 2, 6 (Visit 3, 5)	Week 4, 8 (Visit 4, 6)	Week 12 (Visit 7)	Week 16, 20 (Visit 8, 9)	Week 24 ³ /ET (Visit 10)	Week 28 ⁴ (Visit 11)
Informed consent	X							
Eligibility assessment	X	X						
Demographics	X							
Medical and surgical history	X	X						
Randomization		X						
Physical examination	X	X					X	X
Brief physical examination				X	X	X		
Height	X							
Weight	X	X		X	X	X	X	X
Pregnancy test ⁵	X	X	X	X	X	X	X	X
Tuberculosis test ⁶	X							
Clinical laboratory testing ⁷⁸	X ⁹	X	X	X	X	X	X	X
Lipid assessment ¹⁰		X			X		X	X
HBV and HCV test	X							
12-lead electrocardiogram	X	X			X		X	X
Vital signs	X	X		X	X	X	X	X
Severity of Alopecia Tool (SALT) assessment ¹¹	X	X		X	X	X	X	
Photographs ¹²	X	X			X		X	
Patient Satisfaction Questions	X	X		X^{13}	X		X	
Visual Analog Scale (VAS) for Eyebrows		X			X		X	
Clinical Global Impression of Severity	X	X		X^{13}	X		X	
Clinical Global Impression of Improvement				X ¹³	X		X	
Patient Global Impression of Severity	X	X		X^{13}	X		X	
Patient Global Impression of Improvement				X^{13}	X		X	
Study Product Administration at study site		X	X	X	X	X		
Dispense study drug		X		X	X	X		
Study drug accountability				X	X	X	X	
Adverse events ¹⁴	X	X	X	X	X	X	X	X
Concomitant medications ¹⁴	X	X	X	X	X	X	X	X

	STATISTICAL ANALYSIS PLAN, Final v1.0
Protocol Number CP543.2003	Sponsor: Concert Pharmaceuticals, Inc.

ET=Early termination; HBV= hepatitis B virus; HCV = hepatitis C virus; PPD = purified protein derivative.

- Randomization/Day 1 may occur any time after Screening laboratory results are available and reviewed by the Investigator.
- ² All subsequent visits and week increments should be based on the date of Visit 2. All visit windows are ±3 days for subsequent visits.
- ³ Also serves as the Early Termination Visit for patient withdrawal in this period.
- ⁴ The Safety Follow-Up Visit is intended for those patients who do not roll over into an open-label extension and for patients who have been discontinued from the study and completed the Early Termination Visit (Week 24).

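### For satisfaction and eyebrow VAS, the Week 24 mean difference labelled mITT uses Week 24 observed cases only, and no analysis brings early terminators back in

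*SAP*

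**What the plan says.** **Collection.** Under Protocol 7.3.1, a patient who stops early "should have all Week 24 assessments performed as an Early Termination Visit". The schedule gives Week 24 and ET one column (Visit 10), and its footnote in SAP Appendix 1 reads: "Also serves as the Early Termination Visit for patient withdrawal in this period". Satisfaction and VAS ratings are therefore due at discontinuation.

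**Visit assignment.** SAP 5.4: "Early termination visit assessments will be summarized as a separate visit". SAP 5.3 keeps nominal visits: "For scheduled visits, there will be no reassignment of the analysis visit based on date". It also looks backward only: "Both unscheduled visits and repeat visits will be reassigned to the closest prior visit". No rule moves an earlier rating forward to Week 24.

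**Missing data.** SAP 6.3 applies LOCF and interpolation to SALT, then adds: "All other missing efficacy data as well as missing safety data will not be imputed". SAP 12.2.3, 12.3.1 and 12.3.2 repeat this for each endpoint.

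**Analysis.** SAP 12.5 gives satisfaction, quality and VAS a difference in means with a 90% t-interval at each post-baseline visit, described as "Main analysis: with no imputation based on mITT analysis population". It plans no supportive or subgroup analysis for them. Membership of mITT (SAP 4.1) needs a dose and one post-treatment SALT, not a Week 24 rating.

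**The concern.** The label and the content of the Week 24 row differ. An early terminator can belong to mITT and have ratings at Week 8, Week 12 and ET, yet add nothing to the Week 24 mean difference. The SALT rows of the same table keep that patient through LOCF, so the Week 24 SALT and patient-reported results can describe different patients.

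Patients who stop because of poor regrowth or poor tolerability may also be the less satisfied ones. If so, those who remain look better than the whole arm, and an arm that loses more of them looks better still. Tolerability is part of the primary objective and an intolerable adverse event is a withdrawal criterion (Protocol 7.3), so unequal dropout is possible. Estimation is the study's only efficacy purpose, so a biased point estimate matters.

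**Working it through.** **1. Trace one patient** who stops after the Week 12 visit and attends ET (satisfaction item).

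| Rating | Governing text | Where it is used |
|---|---|---|
| Week 8, Week 12 | SAP 5.3, nominal visit | Week 8 and Week 12 rows |
| ET | SAP 5.4 | Separate ET summary and listing |
| Week 24 | SAP 6.3, not imputed | Missing; patient absent from the Week 24 row |

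A completer with a missing Week 24 form is absent too, so the set is Week 24 observed cases.

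**2. How many.** Protocol 11.1 says: "A sample size of 25 patients (completers) per group provides adequate precision". About 30 per arm are enrolled. The implied allowance is 30 − 25 = 5, and 5/30 = 16.7%. The documents give no SD, target interval width or dropout rate, so there is no precision figure to reproduce. Five is at most the number on this path, because the allowance may include patients outside mITT or lost without an ET visit.

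**3. Bias in closed form.** Let m be the share of an arm missing at Week 24 and g the mean of those observed minus the mean of those missing, in SD units. The observed mean exceeds the full-arm mean by m × g, so the bias in the difference is m₂g₂ − m₁g₁. The documents give neither m by arm nor g; I assume g from 0.5 to 1.0.

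- 5 vs 5, equal g: 0.
- 5 vs 5, a gap in one arm only: (5/30) × 0.5 to 1.0 = 0.08 to 0.17 SD.
- 3 vs 7: (7/30 − 3/30) × 0.5 to 1.0 = 0.07 to 0.13 SD.
- 2 vs 8: (8/30 − 2/30) × 0.5 to 1.0 = 0.10 to 0.20 SD.

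For comparison, the 90% half-width at 25 per arm is t(0.95, 48) × √(2/25) = 0.474 SD. The largest of these biases is 0.20/0.474 = 42% of it.

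**4. Simulation in points on the 5-point item.** Assumed inputs: mean change 0.6, 1.0 and 1.6 at Weeks 8, 12 and 24 in both arms; SD 1.3; between-visit correlations 0.55 to 0.75; 30 per arm; 4,000 trials per scenario. Dropout follows Week 12, with selection weight exp(−k × Week 12 change/SD), k = 1 or 2. The ranges cover both k and several correlation choices.

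| Dropouts | Bias in observed-case difference | In SE (SE about 0.35 to 0.37) |
|---|---|---|
| 5 vs 5 | about 0 (each arm's mean overstated by 0.14 to 0.23) | 0 |
| 3 vs 7 | 0.11 to 0.17 | 0.3 to 0.5 |
| 2 vs 8 | 0.19 to 0.26 | 0.5 to 0.7 |

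The bias favours the arm with more dropout. The nominal 90% interval covers 84 to 87% of the time at 3 vs 7 and 81 to 85% at 2 vs 8. With k = 0 (dropout unrelated to rating), bias is 0.01 or less even at 2 vs 8.

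A likelihood-based estimate using the Week 8 and Week 12 ratings of all patients has bias of about 0.01 or less throughout. Its empirical SD is slightly smaller (0.35 to 0.36 against 0.36 to 0.37).

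**The case against.** The strongest reply is that the plan is open about this. It states three times that nothing is imputed, it reports the number with non-missing data (SAP 6.2), and the endpoints are secondary or exploratory in an estimation-only Phase 2 study. For satisfaction and quality, the text of SAP 12.2.3 and 12.3.2 describes counts, percentages and a shift table; the mean difference appears only in SAP 12.5. All of this is true and limits the weight of the point. It does not supply an analysis that uses the early terminators.

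A second reply is that the bias is conditional. A false difference needs rating-related dropout together with unequal numbers or unequal gaps, and the documents quantify none of these. If tolerability drives dropout and is unrelated to ratings, the difference is unbiased. This stands.

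A third is that the simulation favours the model by construction: dropout depends on an observed rating, and every patient has Weeks 8 and 12. This also stands. The result shows what the model gains when its assumption holds, not that the assumption is true. It is one reason to add the model rather than replace the planned table.

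A reader might also infer that these endpoints are completer-only throughout, or that ET ratings are discarded. Neither follows: the Week 8 and 12 rows (Week 12 for VAS) include patients who leave later, and SAP 5.4 summarises and lists the ET ratings. Nor does the shared Week 24/ET column mean that ET ratings count as Week 24, because SAP 5.4 says otherwise.

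**Conclusion.** The point holds for the Week 24 row of three endpoints: satisfaction, quality and eyebrow VAS. The mean difference there rests on Week 24 observed cases although it is labelled mITT, and no other planned analysis tests that choice.

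The likely size is modest. Under the assumed splits of 3 vs 7 or 2 vs 8 with rating-related dropout, the bias is about 0.1 to 0.25 points on the 5-point item, or 0.3 to 0.7 SE. For the quality score and the VAS, which use other scales, the SD-unit figures apply. The VAS analysis value measures impairment (100 minus the recorded mark), so overstated improvement there means too large a fall.

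It would be tempting to say that about 17% of patients will drop out, or that the plan favours one regimen. The documents support neither: 5 of 30 is inferred from two planning numbers, and no dropout by arm is given. The primary SALT endpoint has its own imputation rule and is not touched by this point. The change is worth making because the ratings are already collected and the cost is small.

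**What to change.** In SAP 12.2.3, 12.3.1, 12.3.2 and the matching rows of 12.5:

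- Add a mixed model for repeated measures for change from baseline, using all scheduled post-baseline ratings: Weeks 8, 12 and 24 for satisfaction and quality, and Weeks 12 and 24 for each eyebrow VAS. Terms: regimen, visit, regimen-by-visit and baseline value. Report the Week 24 difference with its 90% interval.
- Keep the planned table beside it, labelled as observed cases rather than only mITT, with n per visit shown.
- State the mean difference for satisfaction and quality in the section text, so that text and table agree.
- Amend SAP 6.8, which now says covariate adjustment is not applicable, to allow the baseline value.

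Moving ET ratings to the nearest scheduled visit is optional. It departs from the nominal-visit rule in SAP 5.3, and an ET rating that falls nearest an already occupied visit would still go unused.

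The cost is SAP wording and one model per endpoint (per eyebrow for VAS), with no new data or visits. The model assumes that dropout is explained by observed ratings and treats a 5-point item as continuous, as the planned t-interval already does. It cannot use patients with no scheduled post-baseline rating: those who leave before Week 8, or before Week 12 for VAS.
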